### **3.6.6. Planned Analyses**

#### **3.6.6.1. Interim Analysis**

An interim analysis of safety, reactogenicity, and immunogenicity is planned after all participants have completed the Day 29 visit. The interim analysis as of completion of Day 29 will be performed by the study statistician and programmers. The group-level unblinded summary data of the interim analyses may be reviewed by the Sponsor project team for safety monitoring and/or clinical development planning purposes for the mRNA-1083 project. More details will be documented in the study Data Blinding Plan.

#### **3.6.6.2. Final Analysis**

The final analysis will be performed after all participants in Part 2 have completed the Day 181/EoS visit.

#### **4. Changes from Planned Analysis in Protocol**

There are no changes in planned analysis.

## 6. Appendices

### Appendix A Schedule of Activities (SoA)

#### I. Part 1

Visit Number	SCRN	1	2	3	4, 5, 6, 7	8	USV
Type of Visit	C	C	C	C	SC	C	C
Month Time Point	NA			M1	M2-M5	M6	Up to M6
Visit Day	SCRN a	D1 (Baseline) a	D8	D29	D57, D91, D121, D151	D181/ EoS	NA
Window Allowance (Days)	-28	NA	-1 to +3	-7 to +3	±5	±14	NA
Informed consent form, demographics, concomitant medications, medical history	X						
Inclusion/exclusion criteria	X	X					
Blood collection for safety laboratory samples b	X		X				
Full physical examination c	X						
Axillary lymph nodes assessment d		X					
Symptom-directed physical examination e		X	X	X		X	X
Vital sign measurements f	X	X					
Electrocardiogram g		X					
Pregnancy testing h	X	X					
Randomization		X					
Study intervention (including 60-minute, postdose observation period)		X					
Blood collection for humoral immunogenicity i		X		X		X	
Blood collection for cellular immunogenicity j		X		X			
Optional blood collection for genomics j		X					
Optional blood collection for transcriptomics j		X	X	X			
Blood sample for potential cardiac biomarker analysis k		X					
Nasal swab for virus detection l		X					X
Blood collection for SARS-CoV-2 antibodies, nucleocapsid		X					
eDiary activation for recording solicited local and systemic ARs (7 days) m		X					
Review of solicited AR eDiary			X				
Follow-up safety call n					X		

Visit Number	SCRN	1	2	3	4, 5, 6, 7	8	USV
Type of Visit	C	C	C	C	SC	C	C
Month Time Point	NA			M1	M2-M5	M6	Up to M6
Visit Day	SCRN a	D1 (Baseline) a	D8	D29	D57, D91, D121, D151	D181/ EoS	NA
Window Allowance (Days)	-28	NA	-1 to +3	-7 to +3	±5	±14	NA
Recording of unsolicited AEs through Day 29		X	X	X			
Recording of SAEs, AESIs, MAAEs, AEs leading to discontinuation, and concomitant medications associated with these events		X	X	X	X	X	X
Recording of nonstudy vaccinations	X	X	X	X	X	X	X
Study completion						X	

Abbreviations: AE=adverse event; AESI=adverse event of special interest; AR=adverse reaction;; C=clinic visit; COVID-19=coronavirus disease 2019; D=day; ECG=electrocardiogram; EoS=end of study; ILI=influenza-like illness; IM=intramuscular; M=month; MAAE=medically attended adverse event; NA=not applicable; - SAE=serious adverse event; SARS-CoV-2=severe acute respiratory syndrome coronavirus 2; SC=safety (telephone) call; SCRN=Screening; USV=unscheduled visit;

- a. Screening and Day 1 will NOT be performed on the same day. Additionally, the Screening Visit may be performed over multiple visits within the 28-day Screening window.
- b. Safety laboratory tests will consist of total white blood cell count, hemoglobin, hematocrit, platelets, aspartate aminotransferase, alanine aminotransferase, creatinine, alkaline phosphatase, and total bilirubin. Safety laboratory tests will be performed by the central laboratory.
- c. A full physical examination, including height and weight for calculation of body mass index, will be performed at Screening. Additional physical examinations may be performed during the study at the discretion of the Investigator.
- d. On the day of study intervention administration, prior to injection, axillary lymph nodes of the injection arm will be examined, and any abnormalities will be documented.
- e. Symptom-directed physical examinations will be performed at all clinic visits, except at Screening, where a full physical examination will be performed. Interim physical examinations will be performed at the discretion of the Investigator. Any clinically significant finding identified by a healthcare professional during postinjection study visits should be reported as an AE.
- f. Vital sign measurements: Systolic and diastolic blood pressure, heart rate, respiratory rate, and body temperature. The preferred route of temperature assessment is oral. Vital signs must be collected at Screening and on the day of injection (Day 1), once before and at least 60 minutes after injection. Vital signs may be collected at other clinic visits in conjunction with a symptom-directed physical examination. For all vital sign measurements, participant must be seated for 5 minutes before any measurements are taken.
- g. For participants  $\geq 18$  to  $< 51$  years of age only: A 12-lead ECG will be obtained, after 10 minutes of supine rest, at Visit 1/Day 1 prior to injection. The purpose of the ECG is to serve as a stored Baseline comparison, should it be necessary, for subsequent clinical evaluation if a case of suspected myocarditis and/or pericarditis occurs within the conduct of the clinical trial. The ECG output should be filed in the participant's binder. Central reading of the ECG will not be performed. Incidental significant abnormal ECG findings should contribute to the Investigator's assessment of eligibility, at their discretion, as per Exclusion Criterion.
- h. For participants of childbearing potential, a point-of-care urine pregnancy test will be performed at the Screening Visit and before the IM injections on Day 1. At the discretion of the Investigator, a pregnancy test either via blood or point-of-care urine can be performed at any time. For participants of nonchildbearing potential, the follicle-stimulating hormone level may be measured at the Screening Visit, as necessary, and at the discretion of the Investigator, to confirm menopausal status.

- i. Baseline samples for humoral and cellular immunogenicity must be collected prior to receipt of injection on Day 1. Cellular immunogenicity will be sampled and assessed in a subset of participants.
- j. Transcriptomic and genomic samples will be part of the optional biomarker assessment once consented by the study participant. Blood draws on Day 1 must occur prior to participants being administered the study intervention.
- k. For participants  $\geq 18$  to  $<51$  years of age only: Plasma and serum samples will be collected and banked for potential future cardiac biomarker assessment.
- l. A nasal swab to test for the presence of viral respiratory pathogens will be collected prior to the study intervention administration on Day 1 to document any prevaccination infection. A nasal swab should be collected through study completion for protocol-defined ILI or SARS-CoV-2  $\leq 7$  days of symptom onset.
- m. The eDiary activation and entries will be recorded by the participant starting approximately 60 minutes after injection while at the clinic with instruction provided by study staff. Study participants will continue to record in the eDiary each day after they leave the clinic, preferably in the evening and at the same time each day, on the day of injection and for 6 days following injection. Solicited local and systemic ARs will be recorded separately for each injection site.
- n. Trained study staff will call all participants to collect information related to any SAEs, MAAEs, AESIs, AEs leading to study discontinuation, information on concomitant medications associated with those events, and any nonstudy vaccinations.

## II. Part 2

Visit Number	SCRN	1	2	3	4, 5	6	USV
Type of Visit	C	C	SC	C	SC	C	C
Month Timepoint	NA			M1	M3-M5	M6	Up to M6
Visit Day	SCRN a	D1 (Baseline) a	D8	D29	D91, D151	D181/ EoS	NA
Window Allowance (Days)	-28	NA	-1 to +3	-7 to +3	±5	±14	NA
Informed consent form, demographics, concomitant medications, medical history	X						
Inclusion/exclusion criteria	X	X					
Full physical examination b	X						
Axillary lymph nodes assessment c		X					
Symptom-directed physical examination d		X		X		X	X
Vital sign measurements e	X	X					
Electrocardiogram f		X					
Pregnancy testing g	X	X					
Randomization		X					
Study intervention (including 60-minute, postdose observation period)		X					
Blood collection for humoral immunogenicity h		X		X		X	
Optional blood collection for genomics i		X					
Optional blood collection for transcriptomics i		X		X			
Blood sample for potential cardiac biomarker analysis j		X					
Nasal swab for virus detection k		X					
Blood collection for SARS-CoV-2 antibodies, nucleocapsid		X					
eDiary activation for recording solicited ARs (7 days) l		X					
Review of solicited AR eDiary			X				
Follow-up safety call m			X		X		
Recording of unsolicited AEs through Day 29		X	X	X			
Recording of SAEs, AESIs, MAAEs, AEs leading to discontinuation, and concomitant medications associated with these events		X	X	X	X	X	X

Visit Number	SCRN	1	2	3	4, 5	6	USV
Type of Visit	C	C	SC	C	SC	C	C
Month Timepoint	NA			M1	M3-M5	M6	Up to M6
Visit Day	SCRN a	D1 (Baseline) a	D8	D29	D91, D151	D181/ EoS	NA
Window Allowance (Days)	-28	NA	-1 to +3	-7 to +3	±5	±14	NA
Recording of nonstudy vaccinations	X	X	X	X	X	X	X
Study completion						X	

Abbreviations: AE = adverse event; AESI = adverse event of special interest; AR = adverse reaction; BMI = body mass index; C = clinic visit; COVID-19 = coronavirus disease 2019; D = day; EoS = end of study; ILI = influenza-like illness; IM = intramuscular; M = month; MAAE = medically attended adverse event; NA = not applicable; SAE = serious adverse event; SARS-CoV-2 = severe acute respiratory syndrome coronavirus 2; SC = safety (telephone) call; SCRN = Screening; USV = unscheduled visit

- a. Screening and Day 1 may be performed on the same day or a different day. Additionally, the Screening Visit may be performed over multiple visits within the 28-day Screening window.
- b. A full physical examination, including height and weight for calculation of body mass index, will be performed at Screening. Additional physical examinations may be performed during the study at the discretion of the Investigator.
- c. On the day of study intervention administration, prior to injection, axillary lymph nodes of the injection arm will be examined, and any abnormalities will be documented.
- d. Symptom-directed physical examinations will be performed at all clinic visits, except at Screening, where a full physical examination will be performed. Interim physical examinations will be performed at the discretion of the Investigator. Any clinically significant finding identified by a healthcare professional during postinjection study visits should be reported as an AE.
- e. Vital sign measurements: Systolic and diastolic blood pressure, heart rate, respiratory rate, and body temperature. The preferred route of temperature assessment is oral. Vital signs must be collected at Screening and on the day of injection (Day 1), once before and at least 60 minutes after injection. Vital signs may be collected at other clinic visits in conjunction with a symptom-directed physical examination. For all vital sign measurements, participant must be seated for 5 minutes before any measurements are taken.
- f. A 12-lead ECG will be obtained, after 10 minutes of supine rest, at Visit 1/Day 1 prior to injection. The purpose of the ECG is to serve as a stored Baseline comparison, should it be necessary, for subsequent clinical evaluation if a case of suspected myocarditis and/or pericarditis occurs within the conduct of the clinical trial. The ECG output should be filed in the participant's binder. Central reading of the ECG will not be performed. Incidental significant abnormal ECG findings should contribute to the Investigator's assessment of eligibility, at their discretion, as per Exclusion Criterion.
- g. For participants of childbearing potential, a point-of-care urine pregnancy test will be performed at the Screening Visit and before the IM injections on Day 1. At the discretion of the Investigator, a pregnancy test either via blood or point-of-care urine can be performed at any time. For participants of nonchildbearing potential, the follicle-stimulating hormone level may be measured at the Screening Visit, as necessary, and at the discretion of the Investigator, to confirm menopausal status.
- h. Baseline samples for humoral immunogenicity must be collected prior to receipt of injection on Day 1.
- i. Transcriptomic and genomic samples will be part of the optional biomarker assessment once consented by the study participant. Blood draws on Day 1 must occur prior to participants being administered the study intervention.
- j. Plasma and serum samples will be collected prior to the study intervention administration on Day 1 and banked for potential future cardiac biomarker assessment.
- k. A nasal swab to test for the presence of viral respiratory pathogens will be collected prior to the study intervention administration on Day 1 to document any prevaccination infection.
- l. The eDiary activation and entries will be recorded by the participant starting approximately 60 minutes after injection while at the clinic with instruction provided by study staff. Study participants will continue to record in the eDiary each day after they leave the clinic, preferably in the evening and at the same time each day, on

the day of injection and for 6 days following injection. Solicited local and systemic ARs will be recorded separately for each injection site.

m. Trained study staff will call all participants to collect information related to any SAEs, MAAEs, AESIs, AEs leading to study discontinuation, information on concomitant medications associated with those events, and any nonstudy vaccinations.

## Appendix B Analysis Visit Windows

The following applies to Part 1 and Part 2:

Analysis visit windows will be utilized for immunogenicity assessments only.

Data will be mapped using the following approach:

Step 1: If the assessments are collected at a scheduled visit, the collected data will be mapped to the nominal scheduled visit.

Step 2: If the assessments are collected at an unscheduled visit, the collected data will be mapped using the analysis visit windows described in Table 16 below.

If a Participant has multiple assessments within the same analysis visit, the following rule will be used:

- If multiple assessments occur within a given analysis visit, the assessment closest to the target study day will be used.
- If there are 2 or more assessments equal distance to the target study day, the last assessment will be used.

**Table 16 Analysis Visit Windows for Immunogenicity Assessments**

Visit	Target Study Day	Visit Window in Study Day
Day 1	1	1, Pre-vaccination
Day 29	29	[2, 105]
Day 181	181	$\geq 106$

## Appendix C     Imputation Rules for Missing Prior/Concomitant Medications and Non-Study Vaccinations

The following applies to Part 1 and Part 2:

Imputation rules for missing or partial medication start/stop dates are defined below:

a) Missing or partially missing medication start date:

- If only Day is missing, use the first day of the month, unless the start month and year of the medication coincide with the start month and year of the IP injection.
  - If not marked as a prior medication on the Prior/Concomitant CRF page (“Was the medication taken prior to study administration?” = “No”), then use the date of the IP injection.
  - If marked as a prior medication on the Prior/Concomitant CRF page (“Was the medication taken prior to study administration?” = “Yes”), then use the earlier of the first day of the month or the date of the IP injection - 1.
  - If the mark on the Prior/Concomitant CRF page (“Was the medication taken prior to study administration?”) is missing and the medication end date is on/after the date of the IP injection or is missing, then use the date of the IP injection.
- If Day and Month are both missing, use the first day of the year, unless the start year of the medication coincide with the start year of the IP injection.
  - If not marked as a prior medication on the Prior/Concomitant CRF page (“Was the medication taken prior to study administration?” = “No”), then use the date of the IP injection.
  - If marked as a prior medication on the Prior/Concomitant CRF page (“Was the medication taken prior to study administration?” = “Yes”), then use the earlier of the first day of the year or the date of the IP injection -1.
  - If the mark on the Prior/Concomitant CRF page (“Was the medication taken prior to study administration?”) is missing and the medication end date is on/after the date of the IP injection or is missing, then use the date of the IP injection.
- If Day, Month and Year are all missing, the date will not be imputed, but will use the following rules for purposes of determining the status as prior and/or concomitant.
  - If not marked as a prior medication on the Prior/Concomitant CRF page (“Was the medication taken prior to study administration?” = “No”), then the medication will be treated as having begun after IP injection.
  - If marked as a prior medication on the Prior/Concomitant CRF page (“Was the medication taken prior to study administration?” = “Yes”), or if the mark is missing, then the medication will be treated as a prior medication (and as a concomitant medication unless the stop date indicates the medication was stopped prior to IP injection).

b) Missing or partial medication stop date:

- If only Day is missing, use the earliest date of (last day of the month, study completion, discontinuation from the study, or death).
- If Day and Month are both missing, use the earliest date of (last day of the year, study completion, discontinuation from the study, or death).
- If Day, Month and Year are all missing, the date will not be imputed, but the medication will be flagged as a continuing medication.

In summary, the prior, concomitant or post categorization of a medication is described in Table 17 below.

**Table 17 Prior, Concomitant, and Post Categorization of a Medication**

Medication Start Date	Medication Stop Date		
	< Injection Date	≥ Injection Date and ≤ Injection Date + 27 days	> 27 Days After Injection [2]
< Injection Date [1]	P	PC	PCA
≥ Injection date and ≤ 27 days after injection	-	C	CA
> 27 days after injection	-	-	A

A: Post; C: Concomitant; P: Prior

[1] includes medications with completely missing start date

[2] includes medications with completely missing end date

## Appendix D      **Imputation Rules for Missing AE dates**

The following applies to Part 1 and Part 2:

Imputation rules for missing or partial AE start dates and stop dates are defined below:

- a) Missing or partial AE start date:
  - If only DAY is missing, use the first day of the month, unless:
    - The AE end date is after the date of injection or is missing AND the start month and year of the AE coincide with the start month and year of the injection. In this case, use the date and time of injection, even if time is collected.
  - If DAY and Month are both missing, use the first day of the year, unless:
    - The AE end date is after the date of injection or is missing AND the start year of the AE coincides with the start year of the injection. In this case, use the date of injection
  - If DAY, Month and Year are all missing, the date will not be imputed. However, if the AE end date is prior to the date of injection, then the AE will be considered a pre-treatment AE. Otherwise, the AE will be considered treatment emergent.
- b) Missing or partial AE end dates will not be imputed.

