#### **8.4.1. Time Period and Frequency for Collecting AE and SAE Information**

All unsolicited AEs will be collected from the day of study intervention administration through 28 days postinjection.

All AEs leading to study discontinuation, MAAE, SAEs, and AESIs will be collected from the start of study intervention administration until EoS visit at the timepoints specified in the SoA ([Table 1](#) and [Table 2](#)).

All SAEs and AESIs will be recorded and reported to the Sponsor or designee immediately, and under no circumstance should this exceed 24 hours of becoming aware of the event via the EDC. If a site receives a report of a new SAE or AESI from a study participant or receives updated data on a previously reported SAE or AESI and the eCRF has been taken offline, then the site can report this information on a paper SAE/AESI form via the contact information provided on the form ([Section 10.3.10](#)).

An abnormal value or result from a clinical or laboratory evaluation can also indicate an AE if it is determined by the Investigator to be clinically significant. If this is the case, it must be recorded in the source document and as an AE on the appropriate AE form(s). The evaluation that produced the value or result should be repeated until that value or result returns to normal/Baseline or is stabilized and the participant's safety is not at risk.

Investigators are not obligated to actively seek AEs or SAEs after EoS participation. However, if the Investigator learns of any SAE at any time after a participant has withdrawn from or completed the clinical trial and the Investigator considers the event to be reasonably related to the study intervention administration or study participation, the Investigator must promptly notify the Sponsor.

Active and passive surveillance for ILI and COVID-19 will be conducted from Day 1 through EoS. Participants who develop ILI or COVID-19 will be followed through 30 days from the onset of ILI, even if Day 30 is beyond EoS.

Medical occurrences that begin before the start of study intervention but after obtaining informed consent will be recorded as medical history/current medical conditions, not as AEs; however, if the condition worsens at any time during the clinical trial, it will be recorded and reported as an AE.

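### SAP Appendix D dates a partially dated AE that ended on the injection day to before injection, contradicting its own rule for fully missing start dates

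*SAP*

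**What the plan says.** SAP Appendix D applies to Parts 1 and 2 and has three branches for an incomplete AE start date.

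- **Day missing.** "If only DAY is missing, use the first day of the month, unless" an exception holds: "The AE end date is after the date of injection or is missing AND the start month and year of the AE coincide" with those of the injection. The injection date is then used.
- **Day and month missing.** "If DAY and Month are both missing, use the first day of the year, unless" the parallel exception holds: "The AE end date is after the date of injection or is missing AND the start year of the AE coincides" with the injection year. The injection date is then used.
- **Start fully missing.** No date is imputed, but the event is still classified: "However, if the AE end date is prior to the date of injection, then the AE will be considered a pre-treatment AE". In every other case it is treatment emergent.

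For end dates, the appendix says only this: "Missing or partial AE end dates will not be imputed". It does not say how a partial end date is to be compared with the injection date.

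Two other places bear on the point. Protocol 8.4.1 starts AE collection on the injection day, and says that occurrences between consent and injection "will be recorded as medical history/current medical conditions, not as AEs", unless they later worsen. SAP 2.6.3.2 defines a TEAE as an event that was absent before exposure, or that was present and worsened after it. It also says that TEAEs are flagged within the AE listings.

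**The concern.** The exception tests whether the event ended after injection. An end date equal to the injection date is neither after it nor missing, so the default applies and the start is placed before injection. Yet a record on the AE page should, under Protocol 8.4.1, have started or worsened on or after the injection day. The default therefore gives the record a date that the collection rule says it should not have.

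Treatment emergence decides entry to the summary tables of unsolicited AEs, severe AEs, medically attended AEs (MAAEs), AEs of special interest (AESIs) and serious AEs (SAEs). These are primary safety endpoints in both parts. SAP Section 1 says that the SAP prevails where its methods differ from the protocol's, so a programmer would follow Appendix D as written.

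**Working it through.** The plan gives no figure that depends on this rule, so there is none to reproduce. The check passes date patterns through Appendix D. The injection date of 15 April 2024 is my example.

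**Inputs:** the two defaults, the two exceptions, the fully-missing-start bullet and the end-date sentence, all from Appendix D.

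**Rule as coded:** if the known part of the start matches the injection month and year (or the year alone), then start = injection date if end > injection date or end is missing. Otherwise start = 1st of the month (or 1 January).

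| Known start | End date | Resulting start | Class |
|---|---|---|---|
| April 2024 | 14 April | 1 April | pre-injection |
| April 2024 | **15 April** | **1 April** | **pre-injection** |
| April 2024 | 16 April | 15 April | treatment emergent |
| April 2024 | missing | 15 April | treatment emergent |
| April 2024 | May 2024, no day | 15 April | treatment emergent |
| April 2024 | April 2024, no day | 1 April if partial is not missing; 15 April if handled as missing | undetermined |
| 2024 | **15 April** | **1 January** | **pre-injection** |
| none | **15 April** | not dated | **treatment emergent** |

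**Contradiction.** The three bold rows share one end date. With month and year known, or year known, the event is pre-injection; with nothing known about the start, it is treatment emergent. Two branches of one appendix classify the same end date in opposite ways.

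**Boundary.** If injection is on the 1st of the month, the day-missing default equals the injection date and no such event is misplaced. The year-only branch still gives 1 January, which is wrong unless injection was on 1 January.

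**Partial end dates.** Any day in May is after 15 April, so a partial end in a later month or year passes the test. Only a partial end compatible with both sides of injection is open. For that case the result depends on whether partial counts as missing, which the SAP does not say.

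**With an on-or-after test.** The same-day row moves from 1 April to 15 April, the year-only row moves from 1 January to 15 April, and both agree with the fully-missing-start bullet. The 14 April row stays pre-injection. The row with both dates in April and no day is not settled by this change and needs its own sentence.

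**Scale of one record.** If the record is the participant's only event in a table row, dropping it changes the arm percentage by 1/40 = 2.5 percentage points in Part 2, or 1/50 = 2.0 points in Part 1 Cohort A.

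**The case against.** The strongest reply is that the pattern is rare. It needs a known end on the injection day and an unknown start day. Someone who knows that a brief event followed the injection will usually know when it began. Participants are observed for 60 minutes after dosing, solicited reactions go into a daily eDiary, and SAEs and AESIs are reported within 24 hours. On the calendar alone, 14 of the 15 candidate start days from 1 to 15 April precede injection, so the default is not absurd. This stands as to size. It does not rescue the rule, because Protocol 8.4.1 sends an occurrence that began before injection, and did not worsen, to medical history.

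A second reply is that the title of Appendix D speaks of missing dates while its rules cover partial ones, so a partial end date may be meant to count as missing. That is a fair reading, and is why the partial-end case is called ambiguous here. Against it, the end-date sentence names missing and partial separately.

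Appendix C uses an inclusive test for medications ("the medication end date is on/after the date of the IP injection or is missing"). This is weak support, since it is a fallback for when the CRF prior-medication mark is blank.

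A reader might also infer more than the documents support:

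- *That every AE with a partial end date becomes pre-injection.* Those ending in a later month or year do not, and a fully missing end date is covered by the exception.
- *That the rule systematically removes short, early post-injection events.* Nothing in the documents shows that such records exist in number.
- *That fully undated AEs are lost.* They are called treatment emergent, and no stated rule excludes them from the 28-day tables.

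**Conclusion.** Wrong as written, minor. The strict test in both partial-start bullets misclassifies an AE that ended on the injection day. It conflicts with the fully-missing-start bullet of the same appendix and with the collection rule in Protocol 8.4.1. The partial-end case is a gap in the rule rather than an error.

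The effect is confined to the TEAE tables: affected events remain in the AE listings without the flag. The conclusion assumes that the AE page is used as Protocol 8.4.1 describes, and that the event is not classed as treatment emergent by worsening after exposure. The documents give no frequency of partial AE dates, so the total effect cannot be computed. It is probably small.

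**What to change.** In both partial-start bullets of Appendix D, change the end-date test so that the injection date is used when the AE ended on or after the injection date, or when its end date is missing. Then add one sentence: a partial end date that does not establish an end before injection is handled as missing.

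The cost is two short edits, one added sentence and a small change to the derivation code. No new data are needed, and AE counts may rise by a few events.

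Two further changes are not recommended here. Dating every AE with a fully missing start to the injection day would put MAAEs, AESIs and SAEs, which are collected to the end of study, on Day 1 even if they arose months later. The anaphylaxis algorithm in Appendix H is a separate matter and needs no change on this account.
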